2.4 Statistical/Analytical Issues

2.4.1 Adjustments for Covariates

After blind data review, it was decided not to conduct further adjustments for covariates by adding variables.

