5.1.2 Secondary Objectives

- To evaluate the safety and tolerability of 2 fixed doses of Lu AA21004 (10 or 20 mg/day) after 8 weeks of treatment in Japanese patients with MDD.
- To evaluate the efficacy of Lu AA21004 (10 or 20 mg/day) on cognitive functions after 8 weeks of treatment in Japanese patients with MDD.

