6.2.4 Endpoints

MADRS or HAM-D is recommended for efficacy assessments in Guideline for Clinical Evaluation of Antidepressants (Notification No. 1116-1 of PFSB/ELD dated 16 November 2010).^[3] Based on the guideline, the MADRS, which is designed to be sensitive to the changes in severity of core symptom of depression, will be used for the primary endpoint evaluation ^[6], and the HAM-D for the secondary endpoint evaluation in this study.^[7] CGI-S and CGI-I will be used to assess subject's overall severity and improvement of depression.^[8] In addition to these objective assessments of symptoms, SDS will be used in this study to assess patient's subjective treatment effects on social function disabilities due to depression.^[9]

Results of overseas studies of Lu AA21004 showed that Lu AA21004 improved cognitive functions in subjects with MDD. In this study, DSST and PDQ-5 will be used to explore the effect of Lu AA21004 on cognitive functions in Japanese subjects with MDD.

Safety and tolerability of Lu AA21004 will be evaluated by monitoring of AEs, vital signs, weight, clinical laboratory tests, ECGs, and physical examinations. In addition with these safety

evaluations, since it is important to assess suicidal risk for clinical evaluation of antidepressants, suicidal risk will be assessed using C-SSRS at each visit in this study.[\[10\]](#)[\[11\]](#)

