	CGI-S Score at Baseline [Min<= - <=4, 5<= - <=Max]
	SDS Total Score at Placebo Lead-in
	SDS Total Score at Baseline
	DSST Score at Placebo Lead-in
	DSST Score at Baseline
	PDQ-5 Score at Placebo Lead-in
	PDQ-5 Score at Baseline
Analytical	The following summaries will be provided for the above analysis variable(s).
Method(s):	When the randomized set is analyzed, the frequency distribution will be provided for each treatment group and overall. However, weight, BMI, and efficacy endpoints (MADRS total score, HAM-D17 total score, CGI-I score, CGI-S score, SDS total score, DSST score, and PDQ-5 score) will target only the randomized set.
	(1) Frequency distributions for counting values and descriptive statistics for continuous variables

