Descriptive statistics and two-sided 95% confidence intervals of means will be provided for the change from baseline in the DSST score at Week 8 (LOCF) of treatment with double-blind study drug by treatment group. The change from baseline in the DSST score at Week 8 (LOCF) of treatment with double-blind study drug (dependent variable) will be analyzed using an ANCOVA model with treatment as a fixed effect and the baseline DSST score as a covariate. Least Square (LS) means and the two-sided 95% confidence intervals will be provided for each treatment group. The point estimates of the differences in the LS means between each Lu AA21004 group and the placebo group (each Lu AA21004 group - placebo group) and the two-sided 95% confidence intervals will be provided. The differences in the LS means will be tested for treatment differences.

(8) Change from baseline in the PDQ-5 score at Week 8 (LOCF) of treatment with double-blind study drug

Descriptive statistics and two-sided 95% confidence intervals of means will be provided for the change from baseline in the PDQ-5 score at Week 8 (LOCF) of treatment with double-blind study drug by treatment group. The change from baseline in the PDQ-5 score at Week 8 (LOCF) of treatment with double-blind study drug (dependent variable) will be analyzed using an ANCOVA model with treatment as a fixed effect and the baseline PDQ-5 score as a covariate. Least Square (LS) means and the two-sided 95% confidence intervals will be provided for each treatment group. The point estimates of the differences in the LS means between each Lu AA21004 group and the placebo group (each Lu AA21004 group - placebo group) and the two-sided 95% confidence intervals will be provided. The differences in the LS means will be tested for treatment differences.

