DSST score will be analyzed for each visit. Descriptive statistics and two-sided 95% confidence intervals of means will be provided for the observed values and the change from baseline (each post-dose visit - Baseline) in the DSST score at each post-dose visit by treatment group. The change from baseline in the DSST score will be performed based on a mixed model for repeated measurements (MMRM) analysis of covariance with change from baseline (post-dose visit - Baseline) in the DSST score at each post-dose visit (Week 1 to Week 8) as a dependent variable, and visit, treatment group, visit-by-treatment group interaction, baseline DSST score-by-visit interaction as fixed effects. Least Square (LS) means and the two-sided 95% confidence intervals at each visit will be provided for each treatment group. The point estimates of the differences in the LS means between each Lu AA21004 group and the placebo group (each Lu AA21004 - placebo group) and the two-sided 95% confidence intervals will be provided. The change from baseline in the DSST score at each post-dose visit (dependent variable) will be analyzed using an ANCOVA model with treatment as a fixed effect and the baseline DSST score as a covariate. Least Square (LS) means and the two-sided 95% confidence intervals will be provided for each treatment group. The point estimates of the differences in the LS means between each Lu AA21004 group and the placebo group (each Lu AA21004 group - placebo group) and the two-sided 95% confidence intervals will be provided. The differences in the LS means will be tested for treatment differences.

(13) PDQ-5 score

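### Adding the Visit 2 score as a second covariate to the DSST and PDQ-5 models could lower the variance of the cognitive comparisons by about 0% to 20%, at small cost

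*SAP*

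**What the plan says.** Protocol 5.1.2 lists a secondary objective: "To evaluate the efficacy of Lu AA21004 (10 or 20 mg/day) on cognitive functions after 8 weeks of treatment". Protocol 6.2.4 names the instruments, in softer terms: "DSST and PDQ-5 will be used to explore the effect of Lu AA21004 on cognitive functions".

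Protocol 9.3.2, 9.3.3 and Appendix A schedule both scales at Visit 2 (start of the placebo lead-in) and at Visit 3 (the day before double-blind dosing). Protocol 9.3.3 makes Visit 3 the baseline.

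The models use that baseline alone:

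- SAP 2.2 (7), DSST at Week 8 (LOCF): "an ANCOVA model with treatment as a fixed effect and the baseline DSST score as a covariate".
- SAP 2.2 (8), PDQ-5 at Week 8 (LOCF): "an ANCOVA model with treatment as a fixed effect and the baseline PDQ-5 score as a covariate".
- SAP 2.3 (12), the additional DSST MMRM, has visit, treatment group, "visit-by-treatment group interaction, baseline DSST score-by-visit interaction as fixed effects". SAP 2.3 (13) does the same for PDQ-5.

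Protocol 13.1.3 specifies the same two ANCOVAs. The Visit 2 scores appear in the baseline table (SAP 1.2.1, for example "DSST Score at Placebo Lead-in") and in the by-visit summaries of SAP 2.3, but in no model. The optional mediation analysis in SAP 2.3 (15) adds baseline MADRS to the DSST model, not the Visit 2 DSST score.

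SAP 2.4.1 states that "it was decided not to conduct further adjustments for covariates by adding variables". SAP Appendix 1 gives as the reason only that blind review found no covariate to add. Visit 2 scores are not mentioned.

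**The concern.** A single DSST or PDQ-5 score contains measurement error, so adjusting for one score removes less between-subject variation than adjusting for the subject's underlying level would. A second pre-treatment score from about a week earlier carries information about that same level. Because it is obtained before randomisation, using it as a covariate cannot bias the treatment comparison. DSST and PDQ-5 are also not entry criteria, unlike MADRS, HAM-D17 and CGI-S, so the entry thresholds do not directly narrow their range.

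At stake is the width of the confidence intervals, and the chance of seeing an effect, on the two endpoints that answer the cognitive objective. The protocol's power statement covers MADRS only, so no precision is documented for these endpoints.

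**Working it through.** **The plan's own figure.** Protocol 13.3 claims more than 80% power per dose on MADRS with a difference of 3.5, SD 9.5, 160 per group and two-sided level 0.025. The standardised difference is 3.5 / (9.5 × √(2/160)) = 3.295 and the critical value is 2.241, so power is Φ(3.295 − 2.241) = 85.4% (85.1% with the noncentral t). The claim reproduces. It says nothing about DSST or PDQ-5, for which the documents give no SD, effect, correlation or power.

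**Inputs.** 480 subjects in three groups (Protocol 13.3). The correlations are assumptions: r12 between Visits 2 and 3, r13 between Visit 2 and Week 8, r23 between Visit 3 and Week 8.

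**Formulas.** With Visit 3 alone, the residual variance of the ANCOVA is proportional to 1 − r23². With both scores it is 1 − (r13² + r23² − 2·r12·r13·r23)/(1 − r12²). The ratio of the second to the first is 1 − p², where p is the partial correlation of Visit 2 with Week 8 given Visit 3:

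p = (r13 − r12·r23) / √[(1 − r12²)(1 − r23²)]

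With equal correlations r this is p = r/(1 + r). The extra covariate takes residual degrees of freedom from 476 to 475, a variance factor of 476/475 = 1.002. Break-even therefore needs p of only about 0.05.

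**Worked case.** Equal correlations of 0.8 give p = 0.8/1.8 = 0.444 and a ratio of 1 − 0.198 = 0.802. After the degree of freedom it is 0.804. That is like 160/0.804 = 199 subjects per group. An effect with 80% power now (two-sided 5%) would have Φ(2.802/√0.804 − 1.960) = 88%.

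| Assumed r12, r13, r23 | Net variance ratio | Equivalent n per group | 80% power becomes |
|---|---|---|---|
| equal, 0.5 | 0.891 | 180 | 84% |
| equal, 0.6 | 0.861 | 186 | 86% |
| equal, 0.7 | 0.832 | 192 | 87% |
| equal, 0.8 | 0.804 | 199 | 88% |
| equal, 0.9 | 0.777 | 206 | 89% |
| 0.85, 0.68, 0.70 | 0.951 | 168 | 82% |
| 0.85, 0.70, 0.75 | 0.970 | 165 | 81% |
| 0.90, 0.72, 0.75 | 0.978 | 164 | 81% |
| 0.90, 0.65, 0.70 | 0.998 | 160 | 80% |
| first-order decay (r13 = r12·r23) | 1.002 | 160 | 80% |

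**How likely is zero gain?** In the last row Visit 2 tells us nothing beyond Visit 3. If the subject's underlying level itself follows first-order decay, that happens only when Visit 3 is measured without error. With true-score correlations of 0.95 to 0.98 (Visits 2 to 3) and 0.8 to 0.9 (Visit 3 to Week 8), the net reduction is 6% to 11% at reliability 0.8, 3% to 8% at 0.9, 1.5% to 5% at 0.95, and −0.2% at 1.0. These inputs are also assumptions.

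The table is for the ANCOVA with all 480 subjects contributing. The MMRM was not computed separately.

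**The case against.** The planned models contain no error. Same-scale baseline ANCOVA is conventional, it was fixed in Protocol 13.1.3, the SAP follows it, and a blinded review of covariates is on record. SAP 2.4.5 treats all non-primary results as supportive or exploratory, without multiplicity adjustment. All of that stands and limits the point to efficiency.

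The size of the gain is also open to challenge. Visits 2 and 3 are about a week apart and Week 8 is eight weeks later, so equal correlation is close to a best case. Two design features may push the gain down, though this is inference: Visit 2 can follow washout closely, and subjects whose MADRS moved 25% or more between Visits 2 and 3 are excluded, which may make the two scores more redundant. This also stands, and is why the range must start at about zero.

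The argument applies equally to SDS, which is scheduled at both visits, is not an entry criterion and is adjusted for Visit 3 only. That is fair. The point is confined to DSST and PDQ-5 because they serve the named cognitive objective.

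Some stronger readings are not supported:

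- A reader might infer that precision is certainly being lost, and at no cost to recover. The documents give no correlations, and the change carries a degree of freedom, a missing-score rule and a departure from the protocol model.
- A reader might take the Visit 2 score as available for everyone. It is scheduled for everyone. Completeness is not shown, and under SAP 2.4.2 a PDQ-5 total is missing if any item is.
- A reader might suppose that Visit 2 scores were considered and rejected, perhaps because entry criteria restrict baseline range. Neither document says so. The SAP 2.4.1 decision is general, and Appendix 1 says only that there was no covariate to add.

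**Conclusion.** The point holds as a cheap improvement, not as a defect. The DSST and PDQ-5 models leave out a pre-randomisation score of the same scale that the schedule already collects. Including it would lower the variance of the treatment comparison by about 0% to 20%: none under pure first-order decay of the observed scores, about 0% to 5% in the intermediate decay cases, and 11% to 20% with equal correlations of 0.5 to 0.8 (22% at 0.9). A modest gain is the reasonable expectation unless the Visit 3 score is essentially free of error, and the worst case shown is a 0.2% increase. Every one of these figures rests on assumed correlations. No bias is created either way, the endpoints are supportive, and the primary MADRS analysis is unaffected.

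**What to change.** Before unblinding, amend SAP 2.2 (7)–(8) and 2.3 (12)–(13) as follows:

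- Add the Visit 2 (placebo lead-in) score of the same scale as a second covariate, interacting with visit in the MMRM.
- Keep Visit 3 as the baseline from which change is calculated.
- For a subject without a Visit 2 score, use the overall mean of the observed Visit 2 scores, pooled across groups. State this as an exception to SAP 2.4.2 that applies to the covariate only.
- Record the amendment as a change from the models in Protocol 13.1.3. If the sponsor prefers to keep the protocol model in the lead, prespecify the two-covariate model as a supportive analysis.

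The cost is about one sentence per endpoint, one degree of freedom per ANCOVA (two parameters in the by-visit MMRM), the missing-covariate rule and the documented departure from the protocol. No new data are needed.

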2.4.2 Handling of Dropouts or Missing Data

Missing test results and data determined to be non-evaluable according to the Handling Rules for Analysis Data will not be used for hypothesis testing and estimations. When individual items are missing from a multiple-item assessment, the total score will be set to missing. (MADRS total score, HAM-D17 total score, HAM-D21 total score, SDS total score, and PDQ-5 score)

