6. The subject has a MADRS total score at the start of double-blind treatment period that has improved or aggravated by 25% or more from the score at the start of placebo lead-in period.
7. The subject is significantly non-compliant with the study medication in the placebo lead-in period; e.g., not taking the study medication for 6 or more consecutive days.
8. The subject has received electroconvulsive therapy, vagus nerve stimulation, or repetitive transcranial magnetic stimulation therapy within 6 months prior to the screening period, or plans to initiate such therapy during the study.
9. The subject is receiving cognitive-behavioral therapy or psychotherapy at the time of informed consent, or plans to initiate such therapy during the study.
10. The subject is at significant risk of suicide or has a score ≥ 5 on Item 10 (suicidal thoughts) of the MADRS at the start of screening period, the start of placebo lead-in period or the start of double-blind treatment period, or has attempted suicide within 6 months prior to the start of screening period.
11. The subject has experienced any environmental change (e.g. temporary retirement, returnment, change of residence) considered by the investigator to have the potential to impact on the efficacy evaluation, or plans such environmental changes during the study.
12. The subject is currently receiving drug therapy for thyroid dysfunction.
13. The subject is currently receiving hormonal therapy for gynecological disease.
14. The subject has taken excluded medications during the protocol-specified period, or will require to take excluded medications during the study.
15. The subject has previously received vortioxetine.
16. The subject has received study medication in a previous clinical study of Lu AA21004 (including this study).
17. The subject has a clinically significant chronic liver disease.
18. The subject has a history of severe allergy or hypersensitivity to drugs.
19. The subject has a clinically significant unstable illness, for example, hepatic impairment or renal insufficiency, or a cardiovascular, pulmonary, gastrointestinal, endocrine, neurological, rheumatologic, immunologic, infectious, neoplastic, skin and subcutaneous tissue disorders, eye disorders, or metabolic disturbance.

20. The subject has clinically significant abnormal vital signs as determined by the investigator at the start of screening period, placebo lead-in period, or double-blind treatment period.

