Clinical Global Impression Scale (CGI)

The CGI consists of 2 sub-scales: CGI-S and CGI-I.^[8] The CGI-S assesses the physician's impression of the subject's current mental disorder state. The rater should use his/her total clinical experience with this subject population and rate the current severity of the subject's mental disorder on a 7-point scale. The CGI-I assesses the subject's improvement (or worsening). The rater is required to assess the subject's condition relative to baseline* on a 7-point scale. In all cases, the assessment should be made independent of whether the rater believes the improvement is study medication-related or not. Each score of CGI-S and CGI-I should be recorded on the eCRF. Prior to the first rating, potential raters will attend a rating session on concerns to be addressed for the rating of CGI.

* The start day of the double-blind treatment period (Visit 3) is defined as baseline. However, for the assessment at the start of double-blind treatment period (Visit 3) or early termination visit prior to the start of double-blind treatment period, CGI should be assessed comparing with the score at the start of placebo lead-in period (Visit 2).

9.1.8.2 *Social Function Assessment*

Sheehan Disability Scale (SDS)

The SDS is a scale that assesses disabilities in 3 social function domains subjectively.^[9] The subject self-rates the extent to which his or her work/school, social life/leisure activities, and home life/family responsibilities are impaired by his or her symptoms on a 10-point visual analog scale. The SDS also addresses the number of days the above functions were lost or under-productive due to the symptoms. Each item score should be recorded on the eCRF. Prior to the first rating, potential raters will attend a rating session on concerns to be addressed for the rating of SDS.

9.1.8.3 *Cognitive Function Assessments*

Digit Symbol Substitution Test (DSST)

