- Study Day: The day before the first dose of the double-blind study drug will be defined as Study Day -1 and the day of the first dose will be defined as Study Day 1.
- Follow-up Day: The day after the last dose of the double-blind study drug will be defined as Follow-up Day 1.
- Treatment Groups: Placebo, Lu AA21004 10 mg, Lu AA21004 20 mg
- MADRS total score: Sum of the 10 MADRS items
- HAM-D17 total score: Sum of the 17 HAM-D items
- HAM-D21 total score: Sum of the 21 HAM-D items
- SDS total score: Sum of the 3 SDS items
- MADRS response: Percentage of subjects whose MADRS total score decreased by a greater than or equal to 50% from baseline
- MADRS remission: Percentage of subjects whose MADRS total score decreased to 10 or less

Definition of TIME WINDOW

For each test/observation/evaluation item, all evaluable data (non-missing and acceptable according to the “Handling Rules for Analysis Data”) will be handled according to the following rules.

For each visit other than Week 8 (LOCF), observation in the corresponding time interval will be used. If more than one observation lies within the same visit window, the observation with the closest Study Day to the scheduled Study Day will be used. If there are two observations equidistant to the scheduled Study Day, the later observation will be used. The difference from the scheduled Study Day will be judged based on the Study Day and Follow-up Day.

For Week 8 (LOCF), the last observation obtained in the corresponding time interval will be used.

MADRS, CGI-S

Visit	Scheduled Study Day (days)	Time Interval (days)	
		Study Day	Follow-up Day
Screening	Study Day: -22	<= -12	-
Placebo lead-in	Study Day: -8	-11 - -5	-
Baseline (Week 0)	Study Day: -1	-4 - 1	-
Week 1	Study Day: 7	2 - 10	<8
Week 2	Study Day: 14	11 - 21	<8
Week 4	Study Day: 28	22 - 35	<8
Week 6	Study Day: 42	36 - 49	<8
Week 8	Study Day: 56	50 <=	<8
Week 8 (LOCF)	-	2 <=	<8

HAM-D

Visit	Scheduled Study Day (days)	Time Interval (days)	
		Study Day	Follow-up Day
Screening	Study Day: -22	<= -12	-
Placebo lead-in	Study Day: -8	-11 - -5	-
Baseline (Week 0)	Study Day: -1	-4 - 1	-
Week 8	Study Day: 56	2 <=	<8
Week 8 (LOCF)	-	2 <=	<8

CGI-I

Visit	Scheduled Study Day (days)	Time Interval (days)	
		Study Day	Follow-up Day
Baseline (Week 0)	Study Day: -1	<= 1	-
Week 1	Study Day: 7	2 - 10	<8
Week 2	Study Day: 14	11 - 21	<8
Week 4	Study Day: 28	22 - 35	<8
Week 6	Study Day: 42	36 - 49	<8
Week 8	Study Day: 56	50 <=	<8
Week 8 (LOCF)	-	2 <=	<8

SDS

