2.2 Secondary Endpoint(s) and Analytical Methods

Analysis Set: Full Analysis Set

Analysis Variable(s): MADRS response at Week 8 (LOCF) of treatment with double-blind study drug

Analysis Variable(s): MADRS remission at Week 8 (LOCF) of treatment with double-blind study drug

Analysis Variable(s): Change from baseline in the HAM-D17 total score at Week 8 (LOCF) of treatment with double-blind study drug

Analysis Variable(s): CGI-I score at Week 8 (LOCF) of treatment with double-blind study drug

Analysis Variable(s): Change from baseline in the CGI-S score at Week 8 (LOCF) of treatment with double-blind study drug

Analysis Variable(s): Change from baseline in the SDS total score at Week 8 (LOCF) of treatment with double-blind study drug

Analysis Variable(s): Change from baseline in the DSST score at Week 8 (LOCF) of treatment with double-blind study drug

Analysis Variable(s): Change from baseline in the PDQ-5 score at Week 8 (LOCF) of treatment with double-blind study drug

Visit: Week 8 (LOCF)

Analytical Method(s): (1) MADRS response at Week 8 (LOCF) of treatment with double-blind study drug

Frequency distributions will be provided by treatment group along with point estimates and the two-sided 95% confidence intervals for MADRS response at Week 8 (LOCF) of treatment with double-blind study drug. Odds ratios of each Lu AA21004 group to the placebo group (each Lu AA21004 group / placebo group) and the two-sided 95% confidence intervals will be provided and tested for treatment differences using a logistic regression model. The logistic regression model will include MADRS response at Week 8 (LOCF) of treatment with double-blind study drug as a dependent variable, and treatment group and baseline MADRS total score as independent variables.

Analytical Method(s): (2) MADRS remission at Week 8 (LOCF) of treatment with double-blind study drug

Frequency distributions will be provided by treatment group along with point estimates and the two-sided 95% confidence intervals at Week 8 (LOCF) of treatment with double-blind study drug. Odds ratios of each Lu AA21004 group to the placebo group (each Lu AA21004 group / placebo group) and the two-sided 95% confidence intervals will be provided and tested for treatment

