Descriptive statistics and two-sided 95% confidence intervals of means will be provided for the change from baseline in the CGI-S score at Week 8 (LOCF) of treatment with double-blind study drug by treatment group. The change from baseline in the CGI-S score at Week 8 (LOCF) of treatment with

double-blind study drug (dependent variable) will be analyzed using an ANCOVA model with treatment as a fixed effect and the baseline CGI-S score as a covariate. Least Square (LS) means and the two-sided 95% confidence intervals will be provided for each treatment group. The point estimates of the differences in the LS means between each Lu AA21004 group and the placebo group (each Lu AA21004 group - placebo group) and the two-sided 95% confidence intervals will be provided. The differences in the LS means will be tested for treatment differences.

(6) Change from baseline in the SDS total score at Week 8 (LOCF) of treatment with double-blind study drug

Descriptive statistics and two-sided 95% confidence intervals of means will be provided for the change from baseline in the SDS total score at Week 8 (LOCF) of treatment with double-blind study drug by treatment group. The change from baseline in the SDS total score at Week 8 (LOCF) of treatment with double-blind study drug (dependent variable) will be analyzed using an ANCOVA model with treatment as a fixed effect and the baseline SDS total score as a covariate. Least Square (LS) means and the two-sided 95% confidence intervals will be provided for each treatment group. The point estimates of the differences in the LS means between each Lu AA21004 group and the placebo group (each Lu AA21004 group - placebo group) and the two-sided 95% confidence intervals will be provided. The differences in the LS means will be tested for treatment differences.

(7) Change from baseline in the DSST score at Week 8 (LOCF) of treatment with double-blind study drug

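### The SDS total is lost whenever one item is blank, and the plan has no rule for subjects to whom the work/school item does not apply

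*SAP*

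**What the plan says.** SAP 2.4.2 gives one rule for all multi-item scales: "When individual items are missing from a multiple-item assessment, the total score will be set to missing". The scales it lists are "MADRS total score, HAM-D17 total score, HAM-D21 total score, SDS total score, and PDQ-5 score". The SAP Glossary defines the total without any prorating: "SDS total score: Sum of the 3 SDS items". Protocol 9.1.8.2 describes the three items: the subject "self-rates the extent to which his or her work/school, social life/leisure activities, and home life/family responsibilities are impaired" by symptoms.

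The secondary endpoint in SAP 2.2 is "Change from baseline in the SDS total score at Week 8 (LOCF) of treatment with double-blind study drug". It is assessed in the full analysis set (FAS) and "analyzed using an ANCOVA model with treatment as a fixed effect and the baseline SDS total score as a covariate". A subject therefore needs a total at baseline and another after baseline.

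The schedule in Protocol Appendix A places SDS at Visits 2 and 3 and at Visit 8 or early termination. The SAP time-window table for SDS starts the Week 8 (LOCF) interval at Study Day 2. SAP 2.3(11) summarises single SDS items by visit, with differences in mean change and 95% confidence intervals but no baseline adjustment.

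Inclusion criterion 4 admits ages 20 to 75, and no criterion in Protocol 7.1 requires work or study. Employment is not among the demographics listed in Protocol 9.1.2 or the baseline variables in SAP 1.2.1.

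**The concern.** An all-or-nothing rule does little harm on a scale whose items apply to everyone. SDS differs, because one of its items presupposes that the subject works or studies. Retired subjects and homemakers are eligible. If they leave that item blank, the rule discards two domains that were rated.

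SDS is the trial's only measure of social function (Protocol 6.2.4) and a declared secondary endpoint. An analysis labelled FAS could become an analysis of subjects who rated work or school at both visits. No planned table would show this, since work status is not summarised. The planned single-item summaries keep the other two domains, but they are unadjusted and are not the secondary endpoint.

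**Working it through.** **1. Does the rule reach the SDS total?** Yes. SAP 2.4.2 names it, and the Glossary makes it a plain sum of three. Neither document gives a two-item total, a prorated total or a not-applicable code for SDS.

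**2. Can LOCF fill the gap?** No. There is one scheduled SDS assessment after baseline, and the LOCF interval begins at Study Day 2, so neither the baseline nor the Visit 2 value is carried forward. A blank work item at baseline removes the covariate and the change score. A blank at Week 8 removes the outcome.

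**3. The plan's own power figure.** Protocol 13.3 gives none for SDS. For MADRS it claims more than 80% power with 160 per group, SD 9.5 and two-sided 0.025. The standard error is 9.5 × √(2/160) = 1.062.
- At a difference of 3.5: 3.5/1.062 = 3.295, and power = Φ(3.295 − 2.241) = 0.854.
- At 3.0, for either dose, with two statistics correlated 0.5 through the shared placebo arm: 0.858 by simulation.

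Both claims reproduce, and the SDS rule does not touch them.

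**4. Precision of the SDS analysis.** Let f be the share without a usable SDS total, taken as equal across arms. Then n per arm = 160 × (1 − f), and the standard error is multiplied by 1/√(1 − f). The documents give no value of f, so the whole range is assumed. Power per comparison is illustrative only. It uses two-sided 0.05 (SAP section 4) and standardized effects borrowed from the MADRS inputs, 3.5/9.5 = 0.368 and 3.0/9.5 = 0.316.

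| f | n per arm | SE multiplier | Power at 0.368 | Power at 0.316 |
|---|---|---|---|---|
| 0 | 160 | 1.000 | 0.909 | 0.806 |
| 10% | 144 | 1.054 | 0.878 | 0.764 |
| 20% | 128 | 1.118 | 0.838 | 0.714 |
| 30% | 112 | 1.195 | 0.787 | 0.657 |
| 40% | 96 | 1.291 | 0.723 | 0.590 |
| 50% | 80 | 1.414 | 0.644 | 0.515 |

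**5. Bias.** Work status at baseline is fixed before randomization. Losing those subjects narrows the population but leaves a randomized comparison in the rest.

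A blank that first appears at Week 8 is a post-randomization event. As an extreme illustration, take a true standardized difference of −0.30 and remove the worst outcomes in each arm:
- 5% lost in both arms: the estimate stays at −0.30.
- 10% of placebo and 5% of active lost: −0.21.
- 15% of placebo and 5% of active lost: −0.13.

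Heavier loss on active would move it the other way. The documents give no rates, so neither size nor direction can be stated for this trial.

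**The case against.** The strongest objection is that no text says a subject without work or school leaves the item blank. Protocol 9.1.8.2 asks for each item score to be recorded, and item-level conventions may sit in the Handling Rules for Analysis Data, which are not part of the public documents. This stands, and it makes the loss conditional. It does not close the gap, because neither document says what such a subject records.

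A reader might infer that subjects who stop working during the trial drop out because of their outcome. The documents do not support that. The item asks about impairment by symptoms, so someone whose depression ended their work could rate it as maximal. Work can also stop for other reasons. What remains is a possibility: loss may be outcome-related where symptoms end work and the item is then left blank.

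A reader might also assume that many subjects on leave will be enrolled. Exclusion criterion 11 narrows that group. It bars subjects who have had, or plan, "any environmental change (e.g. temporary retirement, returnment, change of residence") that the investigator thinks could affect the efficacy evaluation. It does not reach the long retired, homemakers, or unplanned loss of work after randomization.

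The stakes are limited, too. SDS is one of eight secondary endpoints, SAP 2.4.5 treats everything beyond the primary analysis as supportive or exploratory, and the social and home items are already summarised. This argues for a small change, not for leaving the rule as it is.

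Replacing the three-item total with a rescaled one would go too far. The reason for a blank item is not recorded, so a rule limited to subjects who do not work could not be derived from the data described.

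**Conclusion.** The point holds conditionally. The any-item rule, its application to SDS, the lack of a work/school provision and the failure of LOCF to help are all on the page. That the item is left blank by subjects to whom it does not apply is plausible but not stated.

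If it is left blank, the SDS result loses precision and stops representing the FAS. At an assumed 20% to 40% loss, 128 to 96 per arm remain and the standard error rises by 12% to 29%. That assumes equal loss across arms, an unchanged SD and no other missing data. The randomized comparison is not biased by loss of subjects not working at baseline. Bias from work ending during treatment is possible, but its size and direction are unknown. The primary MADRS analysis and its power are unaffected. The change is worth making because it is cheap and uses data already collected.

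**What to change.** - Keep the three-item total as the prespecified secondary analysis.
- In SAP 2.4.2, add a sensitivity analysis. When only the work/school item is missing at baseline or Week 8, whatever the reason, set the total for that visit to 1.5 times the sum of the other two domains. This gives the missing item the mean of the other two: (a + b) + (a + b)/2 = 1.5(a + b). Then run the same ANCOVA. Applying the rule visit by visit keeps the baseline covariate free of anything that happens after randomization.
- In SAP 2.3(11), analyse change in the social and home items by ANCOVA with treatment and the baseline item score, in all FAS subjects with those items, instead of unadjusted differences only.
- Report the number of subjects with an evaluable SDS total by arm.

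The cost is a few lines of SAP text, one short derivation and two models of a kind the SAP already uses. No new data are needed. The drawback is that some subjects get a rescaled score, on the unverified assumption that work impairment matches the other two domains. A subject whose item is blank at only one visit has a change score that mixes the two versions. Both drawbacks are confined to the sensitivity analysis.
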